8.1.2.1 Hypoglycemic Events

Hypoglycemia not associated with an Adverse Device Effect is only reportable as an adverse event when the following definition for severe hypoglycemia is met: the event required assistance of another person due to altered consciousness, and required another person to actively administer carbohydrate, glucagon, or other resuscitative actions. This means that the participant was impaired cognitively to the point that he/she was unable to treat himself/herself, was unable to verbalize his/ her needs, was incoherent, disoriented, and/or combative, or experienced seizure or coma. These episodes may be associated with sufficient neuroglycopenia to induce seizure or coma. If plasma glucose measurements are not available during such an event, neurological recovery attributable to the restoration of plasma glucose to normal is considered sufficient evidence that the event was induced by a low plasma glucose concentration.

8.1.2.2 Hyperglycemic Events/Diabetic Ketoacidosis

Hyperglycemia not associated with an Adverse Device Effect is only reportable as an adverse event when one of the following 4 criteria is met:

- the event involved DKA, as defined by the Diabetes Control and Complications Trial (DCCT) and described below
- evaluation or treatment was obtained at a health care provider facility for an acute event involving hyperglycemia or ketosis

Hyperglycemic events are classified as DKA if the following are present:

- Symptoms such as polyuria, polydipsia, nausea, or vomiting;
- Serum ketones >1.5 mmol/L or large/moderate urine ketones;
- Either arterial blood pH <7.30 or venous pH <7.24 or serum bicarbonate <15 ; and
- Treatment provided in a health care facility

All reportable Adverse Events—whether volunteered by the participant, discovered by study personnel during questioning, or detected through physical examination, laboratory test, or other means—will be reported on an adverse event form online. Each adverse event form is reviewed by the Medical Monitor to verify the coding and the reporting that is required.

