Severe hyperglycemia mitigation plan	
The study team will receive real time text alerts for CGM values: >180 mg/dL for >1.5 hours or >250 mg/dL for >20 minutes.
	
A study team member will speak with the participant. If ketones are >1.5 mmol/L, or >0.6mmol/L for more than 90 minutes, and not decreasing after an injection of insulin, the site PI or delegated investigator will ascertain whether the participant has the capacity to care adequately for themselves with guidance. If based on clinical expertise and judgement, it appears the participant may not be adequately able to care for themselves without assistance, then the investigator will either directly communicate with someone on the scene whom they judge to have that capacity, or call 911, or both.

Hypoglycemia Mitigation Strategy	
The study team will receive real time text alerts for CGM values <54 mg/dL for >20 minutes
	
A study team member will contact participant to review fingerstick values, discuss etiology of the hypoglycemia, and review with participant the appropriate treatment of the hypoglycemic episode based on glucose level and active insulin on board. A licensed professional on the study team (MD or NP) will direct these clinical decisions.

Severe Hypoglycemia mitigation plan	
The study team will receive real time text alerts for CGM values <54 mg/dL for >20 minutes
	
If the investigator upon contacting a participant due to hypoglycemia notes that she is unable to treat herself or she is unable to be contacted, the

		study investigator will contact her care partner to evaluate the participant and administer glucagon 1mg IM if needed. The investigator or care partner will call 911.

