Emergency Care plan	Study team contacts participant or care partner because of alert or study team is contacted by the study participant or care partner or another individual onsite for an emergent glucose event or a potential ADE or UADE event with a study device	
The event will be reviewed by a licensed professional (MD or NP) on the study team. If the investigator concludes that the participant needs emergency care, the participant will be told to go to an emergency department. Study staff will determine which emergency department the participant will be taken to and follow up within 15 minutes of the expected arrival time to ensure the participant arrived.
 
If the study staff (MD or NP) calls 911, they will remain on the telephone with the participant until the ambulance arrives and speak to the Emergency Medical Technician to provide history and determine where the participant will be taken.

Emergency room visit plan	Study team contacts participant or care partner because of alert or study team is contacted by the study participant or care partner or another individual onsite.	
The PI or designated investigator will speak directly to the emergency room staff caring for the participant.
 
The PI or designated investigator will inform the participant's obstetrician of the emergency room visit

Loss of CGM connectivity	Team will receive a real time text alert for lack of CGM data for > 2 hours	A study team member will speak with the participant. A fingerstick will be performed and troubleshooting will be

		performed as needed to resume CGM activity/connectivity. During this time, the insulin pump will automatically deliver insulin according to the pump's programmed basal insulin delivery settings.
Insulin pump malfunction	
Participant will be alerted by loud beeps from the insulin pump if there is a pump malfunction or a low pump battery. Participant will contact study team if malfunction cannot be remedied within 30 minutes.
 
Real time text alerts will also be sent to study staff for out of closed-loop for 2 hours for any reason.
	
Participant will perform a fingerstick. Troubleshooting will be performed by the study team as needed to resume pump functioning. If the malfunction is not resolved, participant will be instructed to resume her personal pump or initiate subcutaneous insulin treatment as guided by the study MD or NP until the pump is replaced.

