8.1.2 Reportable Adverse Events

For this protocol, a reportable adverse event includes any untoward medical occurrence that meets one of the following criteria:

1. A serious adverse event
2. An Adverse Device Effect as defined in section 8.1.1, unless excluded from reporting in section 8.2
3. An Adverse Event occurring in association with a study procedure
4. Hypoglycemia meeting the definition of severe hypoglycemia as defined below
5. Diabetic ketoacidosis (DKA) as defined below or in the absence of DKA, a hyperglycemic or ketosis event meeting the criteria defined below

Hypoglycemia and hyperglycemia not meeting the criteria below will not be recorded as adverse events unless associated with an Adverse Device Effect. Skin reactions from sensor placement are only reportable if severe and/or required treatment.

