8.4.2 Criteria for Suspending or Stopping Overall Study

In the case of a system malfunction resulting in a severe hypoglycemia or severe hyperglycemia event (as defined in section 8.1.2.2), use of the study device system will be suspended while the problem is diagnosed.

Further, study enrollment will be stopped, and all investigation device use will be immediately discontinued, if:

- Two subjects have an episode of DKA related to system function (includes infusion set failure/occlusion leading to DKA)
- Two subjects have an episode of severe hypoglycemia related to system function
- Two subjects have at any time met criteria to stop the study by showing significant deterioration of glycemic control as determined at any time or during the scheduled weekly contacts, leading to a significant worsening time in range compared to baseline (10% or more worsening of time in target range) and time in range consistently below 50%.

In addition, study activities could be similarly suspended if the manufacturer of any constituent study device requires stoppage of device use for safety reasons (e.g. product recall). The affected

study activities may resume if the underlying problem can be corrected by a protocol or system modification that will not invalidate the results obtained prior to suspension.

The medical monitor for the study will be informed of all serious adverse events and any unanticipated adverse device events that occur during the study and will review compiled safety data at periodic intervals. The medical monitor will request suspension of study activities or stoppage of the study if deemed necessary based on the totality of safety data available. The study medical monitor will be informed of all serious adverse events and any unanticipated adverse device events that occur during the study and will review compiled safety data at periodic intervals. The medical monitor may request suspension of study activities or stoppage of the study if deemed necessary based on the totality of safety data available.

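### As shown, section 8.1.2.2 announces four reporting criteria but lists two, both tied to a health care facility, so persistent ketosis managed at home and judged unrelated and non-serious is not recorded as an AE

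*Protocol*

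**What the plan says.** **Reportable events.** Section 8.1.2 lists five kinds. Item 5 covers DKA or, "in the absence of DKA, a hyperglycemic or ketosis event meeting the criteria defined below". The same section then sets the default: "Hypoglycemia and hyperglycemia not meeting the criteria below will not be recorded as adverse events unless associated with an Adverse Device Effect".

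**The criteria.** Under section 8.1.2.2, hyperglycemia without an Adverse Device Effect (ADE) is "only reportable as an adverse event when one of the following 4 criteria is met". Two bullets follow. One is DKA. The other is "evaluation or treatment was obtained at a health care provider facility for an acute event involving hyperglycemia or ketosis". The DKA definition has several required elements, one of which is "Treatment provided in a health care facility".

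**The home plan.** The severe hyperglycemia row of the contact plan in section 7.2 has this trigger: "If ketones are >1.5 mmol/L, or >0.6mmol/L for more than 90 minutes, and not decreasing after an injection of insulin". The investigator then judges whether the woman can look after herself with guidance. The emergency care row adds: "If the investigator concludes that the participant needs emergency care, the participant will be told to go to an emergency department".

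**Oversight.** Under 6.3 item 5f, the DSMB decides at about 4 weeks on continued use, from a summary of glycemic data and adverse events. Under 8.5 it is told at once of severe hypoglycemia, DKA, device-related SAEs and UADEs. Other ADEs reach it if the Medical Monitor asks, and it reviews compiled safety data periodically.

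**Cross-references.** The suspension rule in 8.4.2 applies to a malfunction that results in severe hypoglycemia or a "severe hyperglycemia event (as defined in section 8.1.2.2"). Section 6.6.2 item 5 bars entry to home use after a severe hyperglycemic adverse event and cites the same section.

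**The concern.** On the text shown, what decides whether a persistent ketone elevation is recorded is where it was treated, not how high it was or whether it responded to insulin. The trigger in 7.2 marks an event the protocol regards as serious enough to question whether the woman can manage alone. Its upper limit, 1.5 mmol/L, is also the serum ketone limit in the DKA definition. At home, pH and bicarbonate would normally not be measured, so the event would not be classified either way.

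The stake is the safety record. Section 7.3.1.5 names DKA as an acute threat to the fetus and notes that in pregnancy it can arise at lower glucose. CGM measures are therefore a weak substitute for ketone information, and none of the three success criteria in 6.3 uses ketones. An event that is not recorded as an AE need not be in the DSMB's summary at about 4 weeks. It also misses the Medical Monitor's causality check, which works from AE forms and reported events (8.1.2.2, 8.1.5, 8.5).

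The second stake is operational. Two safety gates depend on a term that the cited section, as shown, neither uses nor defines.

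**Working it through.** No sample size, power or error rate is involved. The check is a count and a trace through the rules.

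**Step 1: count the criteria in 8.1.2.2.** Announced: 4. Shown: 2. Unaccounted for: 4 − 2 = 2. The stated count cannot be reproduced from the list.

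**Step 2: does either listed criterion work without a facility?**
- DKA: no, because its definition requires facility treatment.
- Facility evaluation or treatment: no, by its own terms. It does cover ketosis without DKA, but only if seen at a facility.

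Listed criteria that can capture ketosis managed at home: 0 of 2.

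**Step 3: does the home plan force a facility visit?** No. A visit follows only if the investigator concludes that emergency care is needed or the woman cannot cope and 911 is called. Management at home is therefore a permitted path after the trigger is met.

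**Step 4: does the exclusion apply?** The ketone trigger sits in a plan set off by CGM alerts (>180 mg/dL for >1.5 hours, or >250 mg/dL for >20 minutes). The event is thus hyperglycemia, and the default in 8.1.2 excludes it unless a criterion or an ADE brings it in.

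**Step 5: trace one illustrative event.** Assume ketones of 2.0 mmol/L, not falling after injected insulin, attributed to intercurrent illness and judged not serious. Section 8.1.3 directs an unrelated verdict where evidence points to such a cause. Items 1 (SAE), 2 (ADE) and 3 (study procedure) then fail by assumption, and item 4 concerns hypoglycemia. Only item 5 is really being tested.

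| Course | Items met in 8.1.2 | Immediate DSMB notice types met in 8.5 |
|---|---|---|
| A. Managed at home | 0 of 5 | 0 of 4 |
| B. Seen in an emergency department, no acidosis, sent home | 1 of 5 (item 5) | 0 of 4 |
| C. Symptoms, pH <7.30 and treatment there | at least 1 of 5 | 1 of 4 (DKA) |

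A and B can be the same ketone result. They differ only in where the woman was assessed.

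**Step 6: the cross-references.** With no definition, at least two readings of severe hyperglycemia are open: every hyperglycemic event reportable under 8.1.2.2, or DKA only. Take course B but caused by a malfunction. The first reading suspends device use under 8.4.2; the second does not. On either reading, malfunction-caused ketosis managed at home falls outside, as shown.

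**Step 7: after the fix.** Course A meets item 5, so 1 of 5. It then goes on an AE form, to the Medical Monitor, and into the DSMB summary.

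**The case against.** The strongest objection is that two bullets may have been lost when the PDF was read, and one of them may be exactly the ketone criterion said to be missing. Nothing in the text settles this. It stands as a condition on the main point.

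Second, the gap is narrow. An ADE is any event the device may have caused or contributed to, with no ketone limit and no facility requirement. Table 8 itself treats raised ketones as pointing to a failed infusion set. Section 8.2 exempts only occlusions that do not lead to ketosis. An investigator can classify an event as an SAE on medical judgment. Home subjects must report positive ketones, and staff responses must be documented. All of this stands: such an event is known to the site. What it lacks is an AE record when the site judges it unrelated and non-serious.

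Third, a reader might infer that 8.1.2.2 contradicts item 5 of 8.1.2. It does not. Item 5 reaches only events that meet the listed criteria, and the second listed criterion does cover some ketosis without DKA.

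Fourth, a reader might infer that 8.5 is defective because it does not require immediate DSMB notice of such ketosis. The documents do not support that. The DSMB sees compiled data periodically, and 8.5 leaves details of its role to a separate charter that is not at hand. Immediate notice of unrelated, non-serious events is a preference.

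Fifth, the zeros in the trace partly follow from its assumptions, and the three success criteria in 6.3 are tied to moving beyond three subjects rather than being the whole review. Both remarks are fair; the weight rests on item 5 alone.

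**Conclusion.** The point holds in limited form and should be corrected; confidence is medium. As shown, the stated count of criteria is wrong by two. Neither listed criterion can capture persistent ketosis managed at home. With the default in 8.1.2, such an event is expressly kept out of AE recording when judged neither device- nor procedure-related nor serious, and need not reach the DSMB's decision at about 4 weeks. This is a stated exclusion, not a detail left for later.

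Its size is one class of event, moving from 0 to 1 of the 5 reportable items once corrected. How often it would occur among up to 21 subjects cannot be derived from the protocol.

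Separately, the meaning of severe hyperglycemia in 8.4.2 and 6.6.2 item 5 is not fixed by the section they cite.

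The conclusion does not extend to the DKA rules. A reader might think the DKA counts in 8.4 should also catch ketosis, but they are written for DKA and apply correctly to it.

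Assumptions: the two listed criteria are the complete list, and the condition about failure to fall after injected insulin applies to both limbs of the 7.2 trigger. If the source file has a ketone-based criterion, the recording gap disappears, and the second point remains only if the term is still undefined there.

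**What to change.** 1. In 8.1.2.2, make the announced number of criteria match the list, and add as reportable, wherever treated: ketones >1.5 mmol/L, or >0.6 mmol/L for more than 90 minutes, not decreasing after an injection of insulin. This is the protocol's own trigger from 7.2.
2. In 8.1.2.2, state which of its events count as a severe hyperglycemia event for 8.4.2 and 6.6.2 item 5. Say expressly whether the >0.6 mmol/L limb counts: it lies below the 1.0 mmol/L above which Table 8 directs an injection. Without this statement, change 1 could silently widen both the suspension rule and the bar to home use.

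Leave the DKA definition and the DKA stopping counts unchanged. Immediate DSMB notice under 8.5 is optional and can be set in the DSMB charter.

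The cost is one added criterion and one clarifying sentence. No new measurement is needed, since positive ketones already go to the investigators and undocumented responses to alerts are already protocol deviations. The downside is a few extra AE forms for events that prove not to be DKA. If the source file already holds a ketone-based criterion, change 1 falls away, and change 2 is needed only if the term is undefined there too.

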8.1.3 Relationship of Adverse Event to Study Device

The study investigator will assess the relationship of any adverse event to be related or unrelated by determining if there is a reasonable possibility that the adverse event may have been caused by the study device.

To ensure consistency of adverse event causality assessments, investigators should apply the following general guideline when determining whether an adverse event is related:

Yes

There is a plausible temporal relationship between the onset of the adverse event and the study intervention, and the adverse event cannot be readily explained by the participant's clinical state, intercurrent illness, or concomitant therapies; and/or the adverse event follows a known pattern of response to the study intervention; and/or the adverse event abates or resolves upon discontinuation of the study intervention or dose reduction and, if applicable, reappears upon re-challenge.

No

Evidence exists that the adverse event has an etiology other than the study intervention (e.g., preexisting medical condition, underlying disease, intercurrent illness, or concomitant medication); and/or the adverse event has no plausible temporal relationship to study intervention.

8.1.4 Intensity of Adverse Event

The intensity of an adverse event will be rated on a three point scale: (1) mild, (2) moderate, or (3) severe. It is emphasized that the term severe is a measure of intensity: thus a severe adverse event is not necessarily serious. For example, itching for several days may be rated as severe, but may not be clinically serious.

- **MILD:** Usually transient, requires no special treatment, and does not interfere with the participant's daily activities.
- **MODERATE:** Usually causes a low level of inconvenience or concern to the participant and may interfere with daily activities, but is usually ameliorated by simple therapeutic measures.
- **SEVERE:** Interrupts a participant's usual daily activities and generally requires systemic drug therapy or other treatment.

8.1.5 Coding of Adverse Events

Adverse events will be coded using the MedDRA dictionary. The Medical Monitor will review the investigator's assessment of causality and may agree or disagree. Both the investigator's and Medical Monitor's assessments will be recorded. The Medical Monitor will have the final say in determining the causality.

Adverse events that continue after the participant's discontinuation or completion of the study will be followed until their medical outcome is determined or until no further change in the condition is expected.

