5.2 Description of Population Studied

The system will be evaluated on up to 21 pregnant adult subjects with type 1 diabetes age 18-45 years old at three clinical sites (Sansum Diabetes Research Institute, Mayo Clinic Rochester MN and Mt Sinai Hospital, New York City). We will recruit pregnant patients between 14-32 weeks gestation. All racial/ethnic groups will be eligible for participation. Subjects will complete a ~48-60 hours closed-loop (CL) session in a supervised outpatient environment with medical staff present, and then have the option to use the CL system at home throughout the remainder of their pregnancy if desired.

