8.5 Independent Safety Oversight

The medical monitor will review all reported adverse events and adverse device events. Additionally the engineering team at Harvard University will be informed of any UADEs that require FDA reporting as defined in section 8.3.

The medical monitor for the study is [name], Maternal Fetal Medicine at Mayo Clinic.

For the extension phase of the study, we have convened a Data and Safety Monitoring Board (DSMB). The DSMB will provide safety oversight. The DSMB will be informed of all cases of severe hypoglycemia and diabetic ketoacidosis irrespective of device relationship, all device-related SAEs, and all UADEs at the time that they occur during the study and will review compiled safety data at periodic intervals. The DSMB also will be informed of any ADEs not meeting criteria for a UADE if the Medical Monitor requests the DSMB review. The DSMB can request modifications to the study protocol or suspension or outright stoppage of the study if deemed necessary based on the totality of safety data available. Details regarding the DSMB's role will be documented in a separate DSMB charter.

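### An SAE that the investigator judged device-related can miss prompt DSMB notice, because the Medical Monitor alone can overrule that verdict (Protocol 8.1.5 with 8.5)

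*Protocol*

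**What the plan says.** Section 8.1.3 has the investigator judge each adverse event related or unrelated to the study device. Section 8.1.5 adds a second assessor: "The Medical Monitor will review the investigator's assessment of causality and may agree or disagree". It continues, "Both the investigator's and Medical Monitor's assessments will be recorded", and then gives the tie-break: "The Medical Monitor will have the final say in determining the causality".

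Section 8.5 sets out what the DSMB, convened for the extension phase, hears about. It is told of every severe hypoglycemia and every DKA regardless of causality. For other serious events the same sentence limits notice to "all device-related SAEs, and all UADEs at the time that they occur during the study". ADEs short of a UADE go to the DSMB only if the Medical Monitor asks. The DSMB also reviews compiled safety data periodically.

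Section 8.5 places the Medical Monitor in "Maternal Fetal Medicine at Mayo Clinic". Section 5.2 lists Mayo Clinic among the "three clinical sites (Sansum Diabetes Research Institute, Mayo Clinic Rochester MN and Mt Sinai Hospital, New York City").

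Sections 8.4.1 and 8.4.2 use relatedness as well. One study-level criterion reads: "Two subjects have an episode of severe hypoglycemia related to system function". DKA has a parallel criterion, and 8.4.1 applies the same qualifier to a single episode in one woman. None of these names the assessor.

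**The concern.** The tie-break works in both directions, so the Monitor may turn an investigator's related into unrelated. For SAEs that are neither severe hypoglycemia nor DKA, that verdict appears to decide whether the DSMB is told at once.

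In this population those SAEs matter. Section 8.1.1 counts death of the fetus, congenital anomaly and inpatient hospitalization as serious. Section 7.3 acknowledges possible unknown risks to mother or fetus. Table 2 shows that adverse pregnancy outcomes are common in type 1 diabetes without this device, and 8.1.3 lets an event be called unrelated when the participant's clinical state explains it. Two careful assessors could therefore differ on exactly these events.

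At stake is how early the DSMB hears of a possible device signal while other women are still using the system at home. A needless notification costs the DSMB a short review. A delayed one may cost time in which others remain exposed.

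**Working it through.** The protocol states no number on this point, so there is none to reproduce. The check is a reading of the sections against each other.

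**Step 1. Whose verdict makes an SAE device-related in 8.5?** Section 8.5 does not say. Section 8.1.3 defines relationship to the study device, and 8.1.5 is the only place that resolves a disagreement about it. The natural reading is that the 8.1.5 outcome applies.

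**Step 2. Which events depend on it?**

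| Event in the extension phase | Prompt DSMB notice under 8.5 | Depends on causality? |
|---|---|---|
| Severe hypoglycemia, DKA | Always | No |
| UADE | Always | Yes: 8.1.1 requires a link to the device |
| Any other SAE | Only if device-related | Yes |
| ADE short of a UADE | Only at the Monitor's request | Yes, and on that request |

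**Step 3. What happens to an SAE in the third row?**

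| Investigator | Medical Monitor | Prompt notice now | With the change proposed below |
|---|---|---|---|
| Related | Related | Yes | Yes |
| Related | Unrelated | Not required | Yes |
| Unrelated | Related | Yes | Yes |
| Unrelated | Unrelated | Not required | Not required |

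Only the second row changes. The extra notifications equal the SAEs in that row, so they cannot exceed the number of such SAEs that investigators call related.

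**Step 4. Cost under an assumption.** Suppose each assessor wrongly calls an unrelated SAE related 10% of the time. This rate is assumed, not taken from the protocol. If the verdicts are independent, the chance that at least one says related is 1 − (1 − 0.10)² = 0.19. If the verdicts always agree, it stays at 0.10. Compared with the Monitor's verdict alone (0.10), the added false notices are 0 to 9 per 100 unrelated SAEs across that range, in a study of at most 21 women.

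**Step 5. The stopping criteria.** The DKA and severe hypoglycemia criteria in 8.4.2 each need two subjects. If the 8.1.5 verdict were the one used, a single downgrade would take a count of two to 2 − 1 = 1 and the criterion would not be met. The protocol does not say that it is the one used. Section 1 also requires a root cause analysis of each event, without naming who performs it. This is a gap in the text, not a demonstrated effect on stopping.

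**The case against.** Several stronger readings are tempting, and the documents do not support them.

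- **A downgrade could hide severe hypoglycemia or DKA from the DSMB.** It could not. Section 8.5 sends all of them, and they are the events that the relatedness-based stops count. The DSMB may stop the study on all the safety data.
- **The Monitor's verdict controls the stops.** That link is inferred. Several stops need no causality verdict: the time-in-range criterion in 8.4.1 and 8.4.2, hospital admission for any reason in 8.4.1, and the immediate study stop in Table 8 for loss of consciousness, seizure or inability to take oral carbohydrates. Under 8.4.1 the investigator can also end a woman's device use on safety grounds alone.
- **A downgraded event disappears.** Both verdicts are kept. Section 8.3 requires every SAE to be recorded within 24 hours, and section 6.3 gives the DSMB a summary including adverse events at about four weeks. What is lost is promptness.
- **Nobody else sees events in the supervised session.** The DSMB is stated only for the extension, but root cause analysis, SAE recording and each site's IRB duties apply to the session too. A severe hypoglycemic or hyperglycemic adverse event there bars entry to the extension (6.6.2) whatever its cause.
- **The Monitor is conflicted.** Only a shared institution is shown. Nothing says that the Monitor belongs to the site's trial team, and the final say can equally upgrade a site's unrelated verdict.

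One may add that details of the DSMB's role are left to a charter not available here, which could already widen notification. That is fair, but 8.5 fixes a notification list in the protocol itself, and for other SAEs that list depends on relatedness. None of these points covers an SAE that is neither severe hypoglycemia nor DKA, which the investigator calls related and the Monitor does not. Hospital admission ends that woman's device use, but it does not alert the DSMB on behalf of the others.

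**Conclusion.** The point holds in a limited form. For SAEs other than severe hypoglycemia and DKA in the extension phase, one person's verdict can withhold prompt DSMB notice of an event that the treating investigator judged related. It affects one of four verdict combinations, and its consequence is delay, not loss.

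This rests on reading device-related in 8.5 as the outcome of 8.1.5, which is the only tie-break the protocol provides. How often it would happen cannot be estimated from the documents. Attaching probabilities to a missed stop would need assumed detection rates and independent verdicts, and independence is doubtful because the Monitor reviews the investigator's assessment.

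A second, smaller point stands by itself: 8.4.1 and 8.4.2 do not say whose judgement makes an event system-related. The change is worth making because both verdicts are already collected and the cost is low.

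**What to change.** Add to 8.5:

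*For notification of the DSMB, an SAE is treated as device-related if either the investigator or the Medical Monitor judges it related. Any SAE on which the two assessments differ is sent to the DSMB with both.*

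The Monitor's final say in 8.1.5 can remain for coding; it would simply no longer decide notification. The DSMB charter should be aligned.

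Separately, reconcile 8.1.5 with 8.4.1 and 8.4.2 so that the protocol states whose verdict applies when events are counted there. No particular stopping rule is proposed.

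The cost is two sentences in an amendment, one clarification and a few extra notifications. No new data are needed.
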